8.3.6. Suicidal Ideation and Behavior Risk Monitoring

Participants being treated with JZP150 should be monitored appropriately and observed closely for suicidal ideation and behavior or any other unusual changes in behavior, especially at the beginning and end of the course of intervention. Participants who experience signs of suicidal ideation or behavior should undergo a risk assessment. All factors contributing to suicidal ideation or behavior should be evaluated, and consideration should be given to discontinuation of the study intervention.

When informed consent has been given, families and caregivers of participants being treated with JZP150 should be alerted about the need to monitor participants for the emergence of unusual changes in behavior, as well as the emergence of suicidal ideation and behavior and to report such symptoms immediately to the study investigator.

Baseline assessment of suicidal ideation and behavior/ intervention emergent suicidal ideation and behavior will be monitored during JZP150-201 using the C-SSRS. At the Screening Visit, the Baseline/Screening Version of the C-SSRS will be administered to participants to exclude any individuals with active suicidal ideation or behavior.

The Since Last Visit Version of the C-SSRS will be administered to participants at every clinic visit after their Screening visit, including the Baseline and Follow-up visits, as well as during telephone calls conducted between clinic visits. At the Screening Visit, any participant who reports active suicidal ideation (eg, a positive response to Question 4 or 5 on the C-SSRS) or behavior (eg, a positive response to any suicidal behavior question on the C-SSRS) will be excluded. At post-baseline visits, active suicidal ideation or behavior must be recorded as an AE and reported to the sponsor or designee within 24 hours of first knowledge of the event by study personnel. Please refer to [Appendix 4](#) for details on reporting other reportable experiences (OREs).

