7.2.3. Analysis Windows

All scheduled, unscheduled, and early termination assessments will be summarized by derived analysis visit per [Table 3](#), regardless of if the visit was performed on-site or remotely. Visit dates will be mapped based on the scheduled period of each visit, with adjusted analysis-defined windows as specified in [Table 3](#).

Height, serum pregnancy, demographics, medical/surgical history, MINI, C-SSRS (screening/baseline version), and Life Event Checklist for DSM-5 (LEC-5) are only assessed at Screening Visit. The analysis window for these assessments is Day -40 up to -2.

CGI-S, PGI-S, CGI-C, PCL-5, and C-SSRS since last visit will be assessed at efficacy and safety follow-up visits. CAPS-5 will be assessed at efficacy follow-up visits (if applicable) but will not be assessed at the safety follow-up visit. PSQI-A, PSQI, ISI, MWC, and PHQ-9 will be assessed at safety follow-up visit but not at efficacy follow-up visits. AEs and prior/concomitant medications are monitored throughout the study.

Jazz Pharmaceuticals
{Statistical Analysis Plan - Protocol #}JZP150-201-02

A clinic visit at the end of Week 8 is also included for safety assessments, secondary efficacy assessments, sparse PK sampling and study intervention dispensation.

If multiple measurements are recorded within a single analysis window, including unscheduled or repeated assessments, early discontinuation assessments, as well as efficacy and safety follow-up assessments, the following rules will be applied to determine the observation from which assessment will be used for that analysis defined visit.

- If there are two or more observations within the same analysis window, then the non-missing observation closest to the scheduled Visit Day will be used in the analysis.
- If two observations are equidistant from the scheduled Visit Day, the on-treatment observation will prioritize over the off-treatment observation, with the exception for safety follow-up visit. If they are both on-treatment observations, then the non-missing observation with the latest collection date will be used in the analysis.
- If two observations are collected on the same day and this day is the closest to the scheduled Visit Day, for efficacy endpoints, the non-missing observation with the earliest collection time will be used in the analysis; for safety endpoints, the non-missing observation with the latest collection time will be included in the analysis.

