Data collected from safety follow-up visit between 7 to 28 days after the last dose can be mapped to the safety follow-up analysis visit. Safety follow-up visits that take place at > 28 days post last dose will be considered out of window and the data collected will not be used.

If an analysis window does not contain any observations, then the data will remain missing for the analysis visit.

Listings will include scheduled, unscheduled, repeated, retest, early termination, efficacy follow-up and safety follow-up data per nominal visits.

Jazz Pharmaceuticals
 {Statistical Analysis Plan - Protocol #}JZP150-201-02

Table 3: Analysis Windows for Assessments or Measurements

Study Period	Scheduled Visit (V)/ Week(W)	Scheduled Visit Day	CAPS-5, SDS ^a	CGI-S, PGI-S, PSQI, PSQI-A ^b , ISI ^b	PCL-5	C-SSRS	CGI-C	MINI, LEC-5, Height, Serum Pregnancy Test	B-IPF ^c , ReQoL-10 ^c , MWC	PHQ-9	SIGH-A ^d , PE	Laboratory, Vital Signs, ECG ^e , Breath Alcohol Test ^e , Urine Drug Screen ^e	Urine Pregnancy Test	Blood Sample PK ^f , AEA, PG ^g
Screening	V1	-40 up to -2	na	na	-40 up to -2	-40 up to -2	na	-40 up to -2	na	-40 up to -2	-40 up to -2	-40 up to -2	-40 up to -2	na
Baseline ^h / Randomization	V2	-1	-1	-1	-1	-1	na	na	-1	-1	-1	-1	-1	-1
Double-Blind Intervention	V3/W1	7±2	na	1-14	1-14	1-7	na	na	1-14	na	1-14	na	1-42	
	V4/W2 (call)	14±2	na	na	na	8-14	na	na	na	na	na	na	na	
	V5/W4	28±2	1-56	15-42	15-42	15-28	1-56	na	na	15-56	1-42	15-42	na	na
	V6/W6 (call)	42±2	na	na	na	29-42	na	na	na	na	na	na	na	na
	V7/W8	56±2	na	43-70	43-70	43-56	na	na	na	na	43-70	43-70	na	43-70
	V8/W10 (call)	70±2	na	na	na	57-70	na	na	na	na	na	na	na	na
	V9/W12	84 (-5, +2)	57-112	71-112	71-112	71-112	57-112	na	1-112	57-112	71-112	71-112	1-112	71-112
Efficacy Follow-up	V11a/W4	28	1-56	1-56	1-56	1-56	1-56	na	na	na	na	na	na	na
	V11/W12	84	57-112	57-112	57-112	57-112	57-112	na	na	na	na	na	na	Na
Safety Follow-up	Safety Follow-up	98(+5)	na	8-112	8-112	8-112	8-112	na	8-112	8-112	na	8-112	8-112	8-112

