- Intervention Period (Day 1 to Day 84 for intervention completers or Day 1 to last dosing day for participants who discontinue intervention early)
- Safety Follow-up Period (> Day 84 for intervention completers or > last dosing day for participants who discontinue intervention early)

If patients have multiple occurrences of a TEAE then it will be counted once for the first occurrence only. For participants who discontinue study intervention prior to study completion, TEAEs occurring after treatment discontinuation will be reported according to the time of first onset.

Only TEAEs are included in summary tables unless otherwise specified. If a participant has multiple episodes of events coded to the same SOC or PT, then the participant will be counted just once in the summaries for that term. For summary tables, participant incidence of TEAEs by SOC and PT are sorted by descending order of frequency of SOC in the JZP150 4 mg treatment arm (then alphabetically for ties) and then by descending order of frequency of PTs within each SOC (then alphabetically for ties). For summaries by PT only, PTs will be sorted in descending order of frequency in the JZP150 4 mg treatment arm. Each TEAE will be summarized by treatment group and pooled JZP150 treatment groups.

For the summary of TEAEs by maximal severity, for each participant, the worst severity recorded by PT and SOC will be used for summary purposes. If severity is missing, the severity level of “severe” will be assumed.

Jazz Pharmaceuticals
{Statistical Analysis Plan - Protocol #}JZP150-201-02

A general overall summary of TEAEs with the number and percent of participants who experienced the following types of events will be provided by treatment group and pooled JZP150 treatment groups:

- Participants with any TEAE
- Participants with any treatment-related TEAE
- Participants with any serious TEAE
- Participants with any treatment-related serious TEAE
- Participants with TEAE by maximum severity
- Participants with an AE outcome as death
- Participants with any TEAE leading to study intervention discontinuation
- Participants with any TEAE leading to study intervention dose interruption
- Participants with at least one TEAE outcome

Participant incidence of TEAEs by SOC and PT will be summarized by treatment group and pooled JZP150 treatment groups for the following:

- TEAEs (by SOC and PT and PT only)
- TEAEs reported in $\geq 2\%$ of participants
- Treatment-related TEAEs
- Serious TEAEs

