10.6.3. Columbia-Suicide Severity Rating Scale

The C-SSRS is a widely used measure of suicidal ideation and behavior. The instrument reliably predicts a potential suicide attempt in those who had previously attempted suicide and is able to determine clinically meaningful points at which a person may be at risk for an impending suicide attempt (Posner et al 2011).

The following summaries will be provided for the C-SSRS data by scheduled visit and by treatment group and pooled JZP150 treatment groups:

- Number and percentage of participants with any suicidal ideation (i.e., having responded yes to any of the 5 types of suicide ideation) as well as broken down by type of suicidal ideation
- Number and percentage of participants with any suicidal behavior ((i.e., having responded yes to any of the 4 or 5 types of suicidal behavior, as applicable) as well as broken down by type of suicidal behavior
- Number and percentage of participants with any suicidal behavior or any suicidal ideation; a participant having reported both suicidal behavior and suicidal ideation will be counted only once
- Number and percentage of participants with self-injurious behavior without suicidal intent.

Missing data will not be imputed. C-SSRS parameters will be summarized by scheduled visit. All C-SSRS parameters will be presented in the participant data listing.

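### C-SSRS analysis windows for Weeks 1 to 10 close on the scheduled day although visits may run 2 days late, so compliant late forms are dropped from the tables or shown under the wrong visit

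*SAP*

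**What the plan says.** SAP 7.2.3 files all scheduled, unscheduled and early termination assessments under a derived analysis visit taken from Table 3. When a window holds several records, one is kept: "If there are two or more observations within the same analysis window, then the non-missing observation closest to the scheduled Visit Day will be used". A window with no record stays missing.

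In Table 3 the C-SSRS windows are Days 1-7, 8-14, 15-28, 29-42, 43-56, 57-70 and 71-112 for Weeks 1, 2, 4, 6, 8, 10 and 12. The Week 2 row reads "V4/W2 (call) 14±2 na na na 8-14": the call may take place up to Day 16, but its C-SSRS window closes on Day 14. The Week 1 row reads "V3/W1 7±2 na 1-14 1-14 1-7": CGI-S, PGI-S and PCL-5 have Days 1-14, while C-SSRS has Days 1-7 for a visit allowed up to Day 9.

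Protocol 8.3.6 fixes the form: "The Since Last Visit Version of the C-SSRS will be administered to participants at every clinic visit after their Screening visit". The same form is used on the calls between visits. SAP 10.6.3 states that "C-SSRS parameters will be summarized by scheduled visit", and its ideation count is any participant "having responded yes to any of the 5 types of suicide ideation". It plans no summary across visits. All C-SSRS data are also listed, and 7.2.3 puts listings on nominal visits.

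**The concern.** The windows and the visit allowances in the same table do not fit together. A visit that the protocol accepts as on schedule cannot be filed under its own visit if it is 1 or 2 days late. What happens to it then depends on when the next visit takes place, which has nothing to do with what the participant answered.

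This matters more for C-SSRS than for a scale measuring current state. A since-last-visit form covers one interval, and the next form starts where it stopped. If a form is discarded, its interval is missing from every C-SSRS table that 10.6.3 specifies. The total of positive responses across those tables can only stay the same or fall.

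The exposure is limited by another rule in Protocol 8.3.6: "At post-baseline visits, active suicidal ideation or behavior must be recorded as an AE". Those events should reach the AE tables, since SAP 10.2 says "Participant incidence of TEAEs by SOC and PT will be summarized by treatment group and pooled JZP150 treatment groups". However, Protocol 8.3.6 illustrates active ideation by Question 4 or 5, whereas 10.6.3 counts all five ideation types. For lower-level ideation, the C-SSRS tables are the planned summary by arm.

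**Working it through.** **Inputs (SAP Table 3).**

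| Visit | Allowed days | C-SSRS window | Late days | Late form falls in |
|---|---|---|---|---|
| Week 1 | 5-9 | 1-7 | 8-9 | Week 2 |
| Week 2 | 12-16 | 8-14 | 15-16 | Week 4 |
| Week 4 | 26-30 | 15-28 | 29-30 | Week 6 |
| Week 6 | 40-44 | 29-42 | 43-44 | Week 8 |
| Week 8 | 54-58 | 43-56 | 57-58 | Week 10 |
| Week 10 | 68-72 | 57-70 | 71-72 | Week 12 |
| Week 12 | 79-86 | 71-112 | none affected | n/a |

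**What the selection rule does.**

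- Next visit on time: Week 1 on Day 9 and Week 2 on Day 14 are both in 8-14, at distances 5 and 0 from Day 14. The Week 1 form is dropped and the Week 1 window is empty.
- Next visit also late: Week 1 on Day 9 and Week 2 on Day 15. Only the Week 1 form is in 8-14, so it is shown as Week 2, and the Week 2 form moves into the Week 4 window.
- Next visit missed: the late form is shown under that next visit.
- Week 10 late: Day 71 or 72 is 13 or 12 days from Day 84. An in-window Week 12 visit is at most 5 days away, so the Week 10 form is always dropped.

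**All allowed patterns.** Six visits with 5 allowed days and Week 12 with 8 give 5^6 × 8 = 125,000 patterns. Not one late Week 1-10 form is filed under its own visit. No on-time or early form is misfiled.

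**Size.** Let p be the chance that each Week 1-10 visit is late, independently, with none missed. A late form at Weeks 1 to 8 is dropped if the next visit is not late; a late Week 10 form is always dropped.

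- Mean dropped per completer = 5p(1−p) + p
- Mean kept under the wrong visit = 5p²
- Chance of at least one dropped = 1 − (1−p)^6, because the last form in any run of late forms is dropped
- Check: 5p(1−p) + p + 5p² = 6p, so every late form is accounted for

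| p (assumed) | Dropped, of 7 forms | Wrong visit | At least one dropped |
|---|---|---|---|
| 5% | 0.2375 + 0.05 = 0.29 (4.1%) | 0.01 | 27% |
| 10% | 0.45 + 0.10 = 0.55 (7.9%) | 0.05 | 47% |
| 20% | 0.80 + 0.20 = 1.0 (14.3%) | 0.20 | 74% |
| 40% | 1.20 + 0.40 = 1.6 (22.9%) | 0.80 | 95% |

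The 40% row is what results if each of the five allowed days is equally likely (2/5 late). It is an upper reference, not a forecast.

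If 10% of visits, including Week 12, are also missed, a form is dropped only when it and the next one both exist. The means are then multiplied by 0.9² = 0.81, giving 0.23, 0.45, 0.81 and 1.30.

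**Positive forms lost.** The planned 188 completers give 188 × 7 = 1,316 forms. Assume 1% to 5% of forms are positive, unrelated to lateness. Lost positives = 188 × mean dropped × positive rate: 0.5 to 2.7 at 5% late, 1.0 to 5.2 at 10%, and 1.9 to 9.4 at 20%. These count forms, not participants.

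**Midpoint windows.** With 1-10, 11-21, 22-35, 36-49, 50-63, 64-77 and 78-112, every allowed day lies in its own visit's window. Over the same 125,000 patterns, none is dropped, misfiled or left empty (unscheduled records aside).

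**The case against.** The strongest reply is about consequence. These are descriptive tables with no formal testing. Listings retain every record. If the denominator is participants with an observation, a dropped form leaves both numerator and denominator, so a by-visit percentage need not be biased. Someone positive at several visits would still appear in other rows. All of this stands, and it keeps the point within the completeness of a safety summary.

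A second reply is that suicidality is captured elsewhere. Protocol Appendix 4 lists suicidal ideation, without a level, for 24-hour reporting, and Protocol 10.1.5 has the safety committee review it. That protects participants and the trial record, but neither is a table by arm. How much lower-level ideation also becomes an AE cannot be judged from the documents.

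Third, scheduled visit in 10.6.3 might mean nominal visit, in which case nothing is lost. SAP 7.2.3 makes this less likely: its derived-visit rule covers all assessments, and Table 3 gives C-SSRS its own column. If nominal visit was meant, 10.6.3 should say so.

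Fourth, the comparison with CGI-S, PGI-S and PCL-5 is imperfect, since those scales are not collected on the calls and have no competing Week 2 window. It is also possible that the C-SSRS windows were meant as calendar intervals, as they largely fit the onset periods for TEAEs in SAP 10.2. But filing is by collection date: a Day 9 form, which mostly describes Week 1, goes to Week 2 and is discarded if the Week 2 call is on time.

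Finally, the lateness and positive rates are assumed. That limits the size estimate, not the filing error, which follows from Table 3 alone.

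**Conclusion.** The concern holds. Under the rules as written, no C-SSRS completed 1 or 2 days late at Weeks 1 to 10 can be tabulated under its own visit, although the protocol allows that timing. At an assumed 5% to 20% late, 4% to 14% of a completer's seven forms would drop out of the tables, and a few more would be mislabelled. This rests on reading the visit in 10.6.3 as the derived analysis visit, and on independent lateness with no missed visits. The effect is confined to the C-SSRS tables, chiefly lower-level ideation. It is worth correcting because a planned suicidality summary should not omit compliant assessments on account of a window boundary.

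**What to change.** 1. SAP Table 3, C-SSRS column: use 1-10, 11-21, 22-35, 36-49, 50-63, 64-77 and 78-112 for Weeks 1, 2, 4, 6, 8, 10 and 12, keeping the present upper bound. State that safety follow-up forms map only to the safety follow-up visit. The Week 12 window runs past the scheduled follow-up on Day 98, so a follow-up form could otherwise stand in for a missed Week 12 visit. If nominal visits were intended, say so in 10.6.3 instead of changing the windows.
2. SAP 10.6.3: add to each C-SSRS table an any-time post-baseline row using all scheduled and unscheduled forms, with post-treatment records identified separately. This restores participant-level counts whichever visit definition is used.
3. Optional, SAP 7.2.3: for C-SSRS only, keep the most severe response within a window rather than the one closest in time, excluding safety follow-up forms from Week 12.

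The cost is edits to one table column and one section, plus the selection rule if item 3 is taken, and minor programming. No new data are needed. Reported counts may rise slightly.

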9.4.5. Safety Analyses

All safety analyses will be made on the Safety Population. All safety analyses will be descriptive; no formal statistical testing will be performed and are further described in the SAP.

Adverse Event Analyses:

Adverse events will be mapped to system organ classes (SOC) and preferred terms using the Medical Dictionary for Regulatory Activities (MedDRA). The participant incidence of AEs, AEs related to study intervention, SAEs, AEs leading to discontinuation, and fatal AEs will be summarized. This overall summary will also provide AEs by maximum severity.

The participant incidence of AEs, AEs related to study intervention, AEs, and AEs leading to discontinuation will also be presented by SOC and preferred term (PT). Preferred term summaries may also be provided.

The participant incidence of an AE will be summarized; if a participant has multiple events with the same PT occurring in different periods, the event will be reported for each of those periods. If an AE continues from one period to the next without increase in severity, the event will be reported only for the period of the AE onset. Changes in the severity of an AE within a period will only be counted as one AE with the worst severity.

Vital Signs:

For each vital sign parameter, summary statistics will be provided for observed and change from baseline values by scheduled visit.

Physical Examinations:

Observed and change from baseline values for weight will be summarized descriptively by scheduled visit.

12-lead ECG:

Observed and change from baseline values for ECG intervals will be summarized descriptively. The number and percent of participants with values or change from baseline values in QT/QTcF exceeding certain thresholds will be tabulated.

Clinical Laboratory Evaluations:

Observed and change from baseline laboratory evaluations will be summarized descriptively.

C-SSRS:

Columbia Suicide Severity Ratio Scale parameters will be summarized by scheduled visit.

Marijuana Withdrawal Checklist

Marijuana Withdrawal Checklist parameters will be summarized by scheduled visit.

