10.4. Vital Signs

The following vital signs measurements will be reported for this study.

- Systolic blood pressure (SBP), (millimeter of mercury [mmHg])
- Diastolic blood pressure (DBP) (mmHg)
- Pulse (beats per minutes [bpm])
- Respiratory rate (breaths/min)
- Temperature (°C)
- Weight (kg)
- Height (cm)
- BMI (kg/m²) [derived as weight (in kg) / [height (in m)]²]

These vital signs (with the exception of the BMI which will be calculated programmatically) will be measured during the Screening Visit and each in-clinic scheduled visit. Height (cm) will be obtained at Screening Visit only.

The following summaries will be provided for vital signs data by treatment group and pooled JZP150 treatment groups by scheduled visit:

- Observed and change from baseline by visit
- Incidence of markedly abnormal criteria (as defined below) by visit

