10.5.2. ECG Abnormal Criteria

Abnormal quantitative ECG measurements will be identified in accordance with the following predefined markedly abnormal criteria ([FDA 2005](#)).

Observed values for QT interval, QTcB interval and QTcF will be classified as follows at each time point:

- > 450 msec (M) or 470 msec (F)
- > 480 msec
- > 500 msec

Change from baseline for QT interval, QTcB interval and QTcF will be classified as follows:

- >30 msec increase from baseline
- >60 msec increase from baseline

A listing of participants meeting markedly abnormal criteria as well as a listing of participants with abnormal ECG overall assessment will also be provided based on the Safety Analysis Set.

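### Safety threshold tables use one selected value per visit window with no any-time post-baseline count, so a crossing seen only at a non-selected assessment is missing from the by-arm figures

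*SAP*

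**What the plan says.** SAP 7.2.3 sends everything through the same windows: "All scheduled, unscheduled, and early termination assessments will be summarized by derived analysis visit per" Table 3. Selection starts as soon as a window holds more than one value: "If multiple measurements are recorded within a single analysis window, including unscheduled or repeated assessments". The order of choice is:

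- Different days: "then the non-missing observation closest to the scheduled Visit Day will be used in the analysis".
- Equal distance: "the on-treatment observation will prioritize over the off-treatment observation, with the exception for safety follow-up visit"; if both are on treatment, the later date is taken.
- Same day, when that day is the nearest: "for safety endpoints, the non-missing observation with the latest collection time will be included in the analysis".

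The section does not separate summaries of means from counts of participants over a threshold.

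The safety sections then define by-visit outputs. SAP 10.4 gives "Incidence of markedly abnormal criteria (as defined below) by visit". SAP 10.5.2 says "Observed values for QT interval, QTcB interval and QTcF will be classified as follows at each time point". SAP 10.3 (shift tables) and 10.6.3 (C-SSRS) are organised by scheduled visit. Protocol 9.4.5 describes a participant-level result for ECGs: "The number and percent of participants with values or change from baseline values in QT/QTcF exceeding certain thresholds will be tabulated".

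**The concern.** One representative value per window suits a mean or a mean change by visit. It does not suit a count of participants who ever crossed a limit, because the selected value is the nearest or latest one and need not be the worst.

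The protocol itself produces extra values. Section 7.1.2 provides for a confirmatory ECG and further ECGs as indicated. Appendix 7 (Table 8) provides for weekly liver tests. Participants who stop early have an early-discontinuation visit. When such a value shares a window with one nearer the scheduled day, it leaves the table.

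The C-SSRS is the clearest case. After Screening the Since Last Visit version is used (Protocol 8.3.6), so each form covers its own interval and one form cannot stand in for another.

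What is at stake is the reported incidence by arm of uncommon safety events. Safety analysis is descriptive only (Protocol 9.4.5), and safety review during the trial is blinded with no independent committee (Protocol 4.1). For these measures, the final tables are therefore the main comparison between arms.

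**Working it through.** There is no figure in the plan to reproduce, so the check applies the rule to concrete cases.

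**Inputs (SAP Table 3).** For laboratory tests, vital signs and ECG, the Week 4 window is Days 15-42 (target Day 28) and the Week 8 window is Days 43-70 (target Day 56). For C-SSRS, the Week 2 window is Days 8-14 (target Day 14) and the Week 4 window is Days 15-28 (target Day 28).

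**Rule.** Keep the value with the smallest |day − target|; for safety data on the same day, keep the latest time.

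| Case (hypothetical values) | Distances | Kept | Result |
|---|---|---|---|
| QTcF 455 msec on Day 28; over 500 msec at an unscheduled ECG on Day 33; early-discontinuation ECG on Day 34 | 0, 5, 6 | Day 28 | Not in the over-500 row |
| Liver tests on Days 28, 35, 42 (Week 4 window) | 0, 7, 14 | Day 28 | A peak on Day 35 or 42 is not in the shift table |
| Liver tests on Days 49, 56 (Week 8 window) | 7, 0 | Day 56 | A peak on Day 49 is not in the shift table |
| C-SSRS positive on Day 20 (unscheduled), negative on Day 28 | 8, 0 | Day 28 | Positive form not counted, although the Day 28 form covers a later interval |
| Abnormal value, then a normal repeat later the same nearest day | equal | the repeat | Abnormal value not counted |
| Abnormal value, then a still-abnormal repeat later the same nearest day | equal | the repeat | **Counted** |
| Abnormal value at the scheduled visit, normal repeat a week later | 0, 7 | scheduled value | **Counted** |
| Unscheduled abnormal value, alone in its window | n/a | that value | **Counted** |

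The rule therefore does not exclude unscheduled values as such. It loses a participant only when every crossing falls on a non-selected assessment.

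**Averaging.** Triplicate ECGs are averaged for each visit (SAP 10.5), as are triplicate blood pressures (Protocol 8.3.2). The latest-time rule therefore bites on separate repeat sets, not within a triplicate. The SAP does not say how the two rules combine.

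**Side effect for C-SSRS.** A scheduled form can also be displaced. A Week 1 visit on Day 9 is within the ±2-day visit window but falls in the Week 2 analysis window, where it loses to a Day 14 call (distances 5 and 0). How often this happens depends on actual visit days, which the documents cannot give.

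**Weight of one participant.** 270 randomised 2:1:2 gives 270 × 2/5 = 108 on placebo, 270 × 1/5 = 54 on 0.3 mg and 108 on 4 mg. One uncounted participant is 1/54 = 1.9 percentage points or 1/108 = 0.9 percentage points. This is the weight of a single case, not an estimate of how many are lost.

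**The case against.** The strongest reply concerns direction. A reader might infer that the rule selectively strips out abnormal results, because abnormal results prompt extra testing. The documents do not support that. When a scheduled value is the abnormal one that triggers repeats, it lies at or near the target day and is kept; the later repeats are what drop out. A net loss needs a first crossing off schedule, or a higher category reached only then, together with a value nearer the target day. No frequency for this is available.

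Second, much is retained elsewhere. Listings include unscheduled, repeated and early-termination data (SAP 7.2.3). Dedicated listings cover laboratory panic values, ALT/AST criteria and markedly abnormal ECGs (SAP 10.3, 10.5.2). New clinically relevant ECG findings, clinically significant laboratory abnormalities, and active suicidal ideation or behavior are to be reported as adverse events (Protocol 7.1.2, SAP 10.3, Protocol 8.3.6). A listing of all values that differs from a one-value-per-visit table is expected and is not a contradiction.

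Third, for QT the by-visit limit is attached only to observed values. The categories for increases over 30 and 60 msec carry no such limit in SAP 10.5.2. Protocol 9.4.5 has none either, and SAP 7.7 lists no change to it. Table shells are not part of the documents.

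All three points stand, and they narrow the concern. They do not remove it. Listings give no incidence by arm. Laboratory and ECG adverse events depend on judgement of clinical significance or relevance. The adverse-event requirement for suicidality concerns active ideation, with C-SSRS items 4 and 5 as its example, and behavior, whereas the C-SSRS table counts any of five ideation types (SAP 10.6.3). The QT wording leaves room for a participant-level count but does not define one.

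**Conclusion.** The point holds in a limited form. As written, the by-visit vital-sign, observed QT/QTc, laboratory shift and C-SSRS summaries can omit a participant whose only crossing or only positive form is at a non-selected assessment, and no any-time or worst-value summary catches that participant. The gap is clearest for C-SSRS.

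The size is unknown. Each such participant would shift an arm's any-time incidence by 1.9 percentage points (0.3 mg) or 0.9 (4 mg). This assumes planned randomised numbers as denominators; the Safety Analysis Set may be slightly smaller. It would be wrong to conclude that serious cases vanish from the report or that incidence is materially understated, since the listings and adverse-event rules keep most of them in view.

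This is a cheap improvement to safety reporting. It does not bear on the efficacy conclusions.

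**What to change.** In SAP 7.2.3, keep the one-value rule for by-visit descriptive statistics and say that it does not govern the rows below. Then:

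- In 10.3, 10.4 and 10.5.2 (observed and change categories), add an any-time post-baseline row, by arm, using the worst value across all scheduled, unscheduled, repeat and early-discontinuation assessments.
- Average each triplicate ECG or blood pressure set first, then take the worst set.
- In 10.6.3, count a participant as positive if any post-baseline C-SSRS form is positive.
- State the period the row covers, in particular whether it includes the safety follow-up visit.

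The cost is SAP wording and modest programming, with no change to data collection. The downside is that counts may be slightly higher, because they include unconfirmed readings and rise with the number of tests. A footnote to the tables should say so.
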